5.2.2 Godin Leisure Time Physical Activity

A 3-item modified version of the Godin Leisure Time Physical Activity Questionnaire

will be used to measure the participants' usual leisure-time exercise habits. It will be administered as part of the survey packet and will be given to the participant during the Screening Visit and the Post-Treatment visit. It is easy to administer and has good test-retest reliability (.81 for total score), and significant correlations with VO_2^{max} . The responses from this survey at baseline will be used to determine if the participant is meeting guidelines for physical activity, as discussed in section 7, and used for randomization.

5.2.3 Accelerometers

At baseline and month 4, participants will wear accelerometers (Actigraph GT3X+) for 7 days to provide an objective measure of physical activity. Before the 16 week assessment staff will mail the accelerometers to participants along with the materials needed for the 24 hour recall interviews. The accelerometer, which will be worn while the participant is awake, is small (1.5 x 2 inches) and can either be clipped to the belt or waistband or placed in a pouch attached to a belt that can be worn under clothing. Cutpoints have been established for light, moderate, hard, and very hard activity [63-65]. Participants also will complete a paper-and-pencil exercise diary each day during the week they wear the accelerometer. The diary will ask participants to indicate what type of exercise was performed, duration of the exercise in minutes, and the effort level during the exercise.

5.2.4 Behavioral determinants

Guide to Health Survey

The Guide to Health survey, developed by Anderson-Bill et al, will be used to measure Social Cognitive Theory-based behavioral determinants (social support, self-efficacy, outcome expectations, and self-regulatory behavior) related to healthy eating patterns and physical. The subscales have very good internal consistency (with the exception of one subscale with an alpha of .66, all are between .77 and .95); they were largely responsive to an online intervention targeting physical activity and healthy eating, and were related to behavior change [66, 67]. The diet self-efficacy scales measure healthy eating patterns (e.g., eating more fruits and vegetables, less fat).

Weight Efficacy Life-style (WEL)

The weight efficacy life-style (WEL) questionnaire will be used to assess the participant's confidence that they can regulate their eating. This scale has been shown to have high internal consistency reliability and is responsive to cognitive-behavioral weight loss interventions [68]; it also partially mediated the effect of a group weight loss intervention for older adults [69]. Also, the Guide to Health scales measure self-efficacy for maintaining an exercise program over time and in a range of situations, but in our study of exercise with endometrial cancer survivors we found that self-efficacy for being able to physically do the exercise (task self-efficacy) was also important [70]. Therefore we will use the exercise self-efficacy

scale from that study (internal consistency reliability = .96), which was based on measures by McAuley [71].

Participant-Reported Outcomes Measurement Information System (PROMIS)

The Participant-Reported Outcomes Measurement Information System (PROMIS) global short form will be used to evaluate the effect of the interventions on participant quality of life. This questionnaire assesses physical function, pain, fatigue, emotional distress, and social healthy domains. The PROMIS global short form has been validated and shown to have similar correlations for the global physical health (GPH) and global mental health (GMH) items as similar items from the SF-36 (36-item short- form health survey) and other measures of health related quality of life [72]. The reliabilities for GPH and GMH were 0.81 and 0.86 respectively which compared to SF-36 at 0.88-0.93 for their physical and mental health items [73]. The advantage to using the PROMIS short form versus the SF-36 is that it takes much less time for the participants to complete.

Self-Administered Comorbidity Questionnaire

Because we will not have medical records readily available for our participants, the Self-Administered Comorbidity Questionnaire will be included in the survey packet and be used to assess comorbidity of the participants. The questionnaire has been validated and has shown moderately strong correlation with the Charleston Index, which was used as a standard [74]. It displayed a Spearman correlation coefficient of 0.55 and kappas exceeding 0.46 for almost every item [74]. This questionnaire should serve as a suitable substitute for the medical record.

Demographic Questionnaire

A basic questionnaire will be used to gather demographic information from each participant and will include questions on race, education, employment, and age.

5.3 Screening Visit 2

Once participant eligibility is confirmed based on the blood test results from Visit 1, participant will be scheduled for Visit 2 in the following order:

- a) Appointment with MD Anderson's Behavioral Research and Treatment Center (BRTC) for anthropometric assessments. The details of these measurements are described below in section 5.3.2.
- b) Laboratory test collection (See Table 5: Study Parameters for the list of laboratory test to be collected for Visit 2).
- c) Appointment in Mays Clinic Gynecologic Oncology for history, physical, and

endometrial biopsy (EMB).

5.3.1 Endometrial biopsy

An endometrial pipelle biopsy will be performed at the Screening Visit 2 and at the 4th month on days 115-125 (plus or minus 10 days) into treatment in all participants from (all four arms) both groups.

In addition to histologic examination, each endometrial biopsy will be examined for proliferation markers as well as other biomarkers. The second biopsy in the no treatment group is important in order to determine variability in the biomarkers due to sampling. In preliminary data from the Wyeth-Ayerst Study, we did see variability in certain transcript levels at the 3 and 6 month time points even in the placebo control group. Therefore, we feel strongly in this study that women in both groups undergo a 4 month EMB.

Risks of office endometrial biopsy are small, and while there are no published data on risk of perforation, we believe that the risk is less than 1/1000. Even in those participants in whom uterine perforation occurs, observation alone is usually sufficient. The severe perforations requiring laparotomy and emergent hysterectomy are not seen in office endometrial biopsies, rather in Dilatation and Curettage (D & C) procedures performed in the operating room.

Participants who have no allergies will be instructed to take orally Non- Steroidal Anti-inflammatory Drugs (NSAIDs) before and after the biopsies to reduce pain and cramping. The NSAIDs medications are available over the counter (See Section 5.2 for the recommended dose).

In the second screening visit, if the patient is experiencing discomfort while the provider is attempting to obtain the endometrial biopsy, we may administer topical lidocaine gel to the cervix. This is supported by prior studies which have demonstrated that patients may experience less pain with tenaculum placement and cervical dilation when topical lidocaine is used (Hassan et al, 2005; Davies et al, 1997). Occasionally, some patients may have cervical stenosis, which makes it difficult to dilate the cervix, insert the endometrial suction curette, and obtain an endometrial biopsy. In these instances, prior studies have suggested that the use of vaginal misoprostol may soften the cervix and increase the likelihood that the cervix can be dilated so that the procedure can be performed (Bastu et al, 2013; Ghosh et al; 2013). If cervical stenosis is encountered during the second screening visit, and the study gynecologist is unable to pass the curette or dilator through the cervix, the participant will be given a prescription for misoprostol 200mcg #2 tablets and re-scheduled to return to the clinic for a repeat attempt at performing the endometrial biopsy (within 10 days). The participant will be given instructions to self-administer 1 tablet intravaginally the night before the procedure and one tablet the morning of the procedure. Both lidocaine jelly and misoprostol will be administered as needed. Research Nurse will counsel the participant on the common symptoms of these agents prior to the second screening visit.

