This study will use a 2 x 2 randomized design with all 100 post- menopausal subjects being randomized to metformin, placebo, placebo and intensive lifestyle intervention, or metformin and intensive lifestyle intervention. Treatments will last 4 months. Participants will be assessed at baseline and end of treatment with endometrial sampling to see if there are changes in the biomarkers.

Protocol Sections

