3.4 Dose and Duration of exposure

Table 2: Monthly Dosage of Metformin or Placebo capsule(s)

	Week 1	Week 2	Week 3	Week 4
1 st Month	One capsule daily	One capsule 2X daily	One capsule 3X daily	Two capsules 2X daily
2-4 Month	Two capsules 2X daily	Two capsules 2X daily	Two capsules 2X daily	Two capsules 2X daily

- Orally for 120 days (plus or minus 10 days).
- The dose of metformin hydrochloride will be in 425 mg capsule(s) by mouth, the dose used in The Diabetes Prevention Program Randomized Trials.[50]

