6.1 Treatment

Prior to beginning therapy, participants will have a baseline endometrial biopsy performed. If the baseline endometrial biopsy reveals endometrial hyperplasia or cancer or if an office endometrial biopsy cannot be performed the participant will be removed from study. Women with abnormal biopsy results will be referred to contact their Gynecologist from their insurance provider for further treatment for these results.

The study is partially blinded in that investigator and participants will be blinded to the treatment of Metformin versus placebo, but will be un-blinded in regard to the lifestyle intervention. All participants will be followed for at least one month after their last dose of study medication. All treatment-related toxicities will be followed by phone until resolution. All other participants will be randomized to one of four arms:

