6.1.1 Metformin and Lifestyle Intervention

- These participants will have a baseline endometrial biopsy.

- See Table 2 in section 3.4 for Metformin Monthly dose and duration.
- Second EMB and post study labs will be done between days 115-125 (plus or minus 10 days).
- For the lifestyle intervention, all participants will receive the intervention described below in section 6.2.

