6.1.3 Metformin and No Lifestyle Intervention

- These participants will have a baseline endometrial biopsy.
- A total of four 30 day cycles (plus or minus 10 days) will be given (120 days).
- See Table 2 in section 3.4 for Metformin Monthly dose and duration.
- The second EMB, as well as post study labs will be done between 115-125 days (plus or minus 10 days).

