8.0 Criteria for Removal from the Study

- 8.1 Subjects are free to leave the study at any time.
- 8.2 Participants may be removed from the study at the discretion of the investigator if there is sufficient reason to suspect that the participant is not compliant with the study requirements.
- 8.3 If at any time during the study, the participant experiences symptoms of congestive heart failure or renal failure, drug will be stopped and the participant taken off study.
- 8.4 Abnormal baseline endometrial biopsy or the endometrial biopsy is unable to be performed.
- 8.5 Non-compliance: Non-compliance will be defined as a participant missing more than 4 consecutive doses per month or a total of more than 10 doses during the 4 month period.
- 8.6 Lost to follow-up: Diligent attempts must be made by telephone and letter to determine the circumstances for loss to follow-up, since loss may be related to study drug.

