13.0 Schedule of Events

Table 5: Study Parameters (see next page)

Study Parameters	TAT ^a	Tube Top	Screening	Screening	Randomization	1 st Month	2 nd Month	3 rd Month	4 th Month	1 yr.
		Color	Visit 1	Visit 2	Visit 3	^b	^b	^b	^b	Follow-Up
Informed Consent			X							
History				X						
Physical				X		X				
Research Red Tube ^c		Red	X						X	X
Research Lavender Tube ^c		Lavender	X						X	X
Insulin (fasting)	4 days	Red	X						X	X
Glucose (fasting)	4 hrs	Mint	X						X	X
FSH (Spec Chem Test)	24 hrs	Gold	X						X	X
Hemoglobin	4 hrs	Lavender	X						X	X
Estradiol	5 days	Red		X					X	X
Estrone	5 days	Red		X					X	X
Testosterone (Chem Test)	24 hrs	Gold		X					X	X
DHEA-S	5 days	Red		X					X	X
Sex Hormone Binding Globulin (SHBG)	5 days	Red		X					X	X
Adiponectin	7 days	Red		X					X	X
A1C (Spec Chem Test)	24 hrs	Lavender	X						X	X
IGF-1	7 days	Red		X					X	X
Serum Creatinine	4 hrs	Mint	X			X			X	X
ALT	4 hrs	Mint	X			X	f	f	X	X
Triglycerides (fasting)	4 hrs	Mint	X						X	X
TSH	24 hrs	Gold	X						X	X
Dispense Medication & Pill					X	X	X	X		
Pill Count						X	X	X	X	
Pre-treatment EMB	72 hrs			X						
Toxicity and Compliance Assessment: Phone ^e						X	X	X	X	
Toxicity Assessment: In-person						X	X	X	X	
Post-treatment EMB	72 hrs								X	
DEXA				X					X	X
waist circumference				X					X	X
hip circumference				X					X	X
BMI				X					X	
ASA-24 (3) ^d			X						X	
Accelerometer			X						X	
Survey Packet				X					X	X

a) Turn Around Time

b) Plus or minus 10 days.

c) Research blood for future biomarker analysis.

d) 1 ASA-24 completed at Screening Assessment. Other 2 ASA-24s complete randomly between screening assessment and 7 days post-biopsy.

e) As needed

f) Only if ALT levels elevated as listed in CTCAE version 4.0.

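### No rule keeps women on capsules until the second biopsy, so the Ki-67 sample may be taken off metformin: up to 5 days in the nominal window, 15 with the tolerance

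*Combined protocol and SAP*

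**What the plan says.** **Dosing.** Section 3.4 gives the duration as "Orally for 120 days (plus or minus 10 days". Section 6.1.3 puts it as cycles, "A total of four 30 day cycles (plus or minus 10 days) will be given (120 days", and section 6.1.4 does the same.

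**Second biopsy.** Section 5.3.1 sets it "at the 4th month on days 115-125 (plus or minus 10 days) into treatment in all participants". Section 6.1.1 repeats the window and adds the blood tests, "Second EMB and post study labs will be done between days 115-125 (plus or minus 10 days", and sections 6.1.2 to 6.1.4 give the same days. In Table 5 the post-treatment biopsy sits in the month-4 column, whose footnote reads "b) Plus or minus 10 days".

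**Links between the two.** The synopsis says "Participants will be assessed at baseline and end of treatment with endometrial sampling". Only one interval is counted from the last dose, the safety follow-up in section 6.1: "All participants will be followed for at least one month after their last dose of study medication".

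**Supply and compliance.** Table 5 dispenses at Visit 3 and months 1 to 3 and only counts pills at month 4. Under section 6.4, unused pills come back at every clinic visit. No supply quantity is stated. Section 8.5 defines non-compliance as "missing more than 4 consecutive doses per month or a total of more than 10 doses during the 4 month period".

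**The concern.** Both windows are expressed in days of treatment, and neither refers to the other. Staff who follow the written days can stop a woman's capsules on day 120 and biopsy her later without any deviation.

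That matters because of what is measured at that visit. Ki-67 is the primary endpoint (section 1.2.1). The four phospho-proteins were chosen as markers of metformin's action (section 1.1.2.2). Fasting insulin and glucose are drawn at the same month-4 visit. Section 6.0 justifies four months of treatment as the time metformin needs for its full effect on insulin resistance, and a sample taken after the drug has cleared sits badly with that reasoning. Any loss from washout would fall on the two metformin arms alone. The analysis could not repair it, because the affected woman has no on-drug sample.

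**Working it through.** **Inputs.** Dosing of 120 days with a tolerance of 10 (3.4, 6.1.3, 6.1.4). Biopsy on days 115-125 with a tolerance of 10 (5.3.1, 6.1.1 to 6.1.4). Month 4 with a tolerance of 10 (Table 5). Half-life 17.6 hours in blood and 6.2 hours in plasma (3.5). Two capsules twice daily from week 4 (Table 2). Planned mean decreases of 0, 3.5, 1.75 and 7 with SD 0.8 (9.0), and 25 women per arm (5.4).

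1. **Plan's own figure.** 4 cycles × 30 days = 120 days, which agrees with section 3.4.
2. **Windows.**
   - Dosing ends on days 120 − 10 = 110 to 120 + 10 = 130.
   - Biopsy falls on days 115 − 10 = 105 to 125 + 10 = 135.
   - Table 5, with 30-day months, gives 110 to 130.
3. **Gap = biopsy day minus last capsule day, for a woman who completes 120 days.**
   - Nominal window: 115 − 120 = −5 to 125 − 120 = +5.
   - Table 5 window: −10 to +10.
   - Full window: −15 to +15.
   - Negative gaps are on-drug samples and do no harm.
4. **Past the longest dosing.** Days 131-135 follow day 130, so a biopsy there is off drug by 1 to 5 days even for a woman dosed to the limit.
5. **Drug remaining.**
   - 5 days = 120 h. In blood, 120 / 17.6 = 6.8 half-lives, and 0.5^6.8 ≈ 0.9% is left. In plasma, 120 / 6.2 = 19.4 half-lives.
   - 15 days = 360 h, and 360 / 17.6 = 20.5 blood half-lives, so essentially nothing is left.
   - This describes the drug, not the markers. The documents give no reversion rate for Ki-67, the phospho-proteins or insulin.
6. **Power under the planned means.**
   - Metformin contrast = (3.5 + 7)/2 − (0 + 1.75)/2 = 4.375.
   - SE = 0.8 × √(4/100) = 0.16, so the contrast is 27 SE.
   - Extreme bound, by assumption only: every woman stops on day 120, biopsies spread evenly over days 105-135, and the effect vanishes entirely off drug. The off-drug share is then p = 15/31 = 0.484, and the contrast is 4.375 × 0.516 = 2.26.
   - Mixing on- and off-drug women adds p(1 − p)δ² to the variance in each metformin arm, with δ = 3.5 for metformin alone and 7 − 1.75 = 5.25 for the combination. The variances are 0.64 + 0.25 × 12.25 = 3.70 and 0.64 + 0.25 × 27.56 = 7.52.
   - SE = √[(3.70 + 7.52 + 0.64 + 0.64)/(4 × 25)] = 0.354. The contrast is still 2.26/0.354 = 6.4 SE, with power above 99%.
7. **Capsules to cover a late biopsy.** To day 130: 10 days × 4 = 40. To day 135: 15 × 4 = 60.

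**The case against.** The strongest reply is that on-drug sampling is what the protocol means. The biopsy is timed into treatment and at its end. The pill count and return of leftover pills share the month-4 visit. The dosing tolerance of 10 days matches the visit tolerance, so dosing may simply flex with the visit. On that reading nothing is lost. I accept that this is the likely intention. It is still not written as a rule. Other wording points the other way: section 2.6 places the biopsy after four months of therapy, and Table 5 labels it post-treatment. Matching tolerances also cannot cover days 131-135.

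A second reply is that section 8.5 catches the gap. If dosing is due up to the visit, stopping 5 days early misses 5 × 2 = 10 consecutive doses, above the limit of 4. But section 8.5 counts missed doses within the 4-month period and does not clearly reach days after a completed 120-day course.

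A third is that the clocks may differ. Section 6.4 counts monthly visits from Visit 3, when the prescription is issued. If the biopsy follows that clock, a late first capsule moves it toward on-drug. That is fair, but it narrows the gap only by the length of the delay.

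A fourth is that the Pill Diary and the database in section 7.2 already hold the data needed to derive the interval. That also stands: only the tabulation is new.

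**Conclusion.** The point holds as a cheap improvement to the timing of the primary sample. For a compliant woman the written windows allow a gap of up to 5 days off drug nominally and up to 15 with the biopsy tolerance. Days 131-135 lie beyond any permitted dosing. The gaps of 5 and 15 days assume a last capsule on day 120.

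Four stronger readings are tempting, and the documents do not support them.

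- **Gaps of up to 25 days.** These need a stop on day 110 and a biopsy on day 135. By day 120 that stop misses 10 × 2 = 20 doses, against section 8.5's limits of 4 consecutive and 10 in total. The point does not rely on it.
- **A known percentage dilution.** Counting off-drug days (5 of 11, or 15 of 31) counts calendar days, not women. Turning it into bias needs a hard stop on day 120, even scheduling and a reversion fraction, none of which the plan gives. The size is unknown, and it is zero if capsules are taken until the visit.
- **Bias that can only favour placebo.** Loss toward zero is the most plausible direction, but the documents say nothing on marker behaviour after withdrawal, so rebound cannot be excluded.
- **An underpowered trial.** Under the planned means it is not, even at the extreme bound. That check does not settle the smaller effects also mentioned in section 9.0.

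What the fix buys is a cleaner estimate, and a null result that cannot be put down to washout.

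**What to change.** State in sections 3.4, 5.3.1 and 6.1 that capsules continue through the day of the post-treatment biopsy and labs. Let the dosing tolerance and the month-3 supply cover the booked date, which means allowing dosing to day 135 if the biopsy window stays as it is. Tabulate the interval from last capsule to biopsy by arm, from the Pill Diary and the dosing and biopsy records already planned in section 7.2.

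The cost is a sentence in three sections and one table, with no new visit, assay or data field. Women booked after day 120 take a few more days of capsules: at most 40 extra at day 130 and 60 at day 135.

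Aligning the biopsy window with Table 5 (days 110-130) is optional. It removes the mismatch but cuts scheduling room for an invasive procedure from 31 to 21 days, and it is not needed once capsules continue to the visit.

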5.3.2 Anthropometric assessments

BRTC staff will measure the participants' height, weight, and waist circumference at baseline and 4th month. Height will be measured by having the participant stand evenly without shoes on a flat surface at a right angle to the movable vertical board or cap that is pulled down to lightly touch the most superior point of the head. Weight will be measured using either a standard beam scale or an electronic digital scale. The scale should be on a level floor, and participants should be gowned or wearing light clothing and no shoes. Waist circumference will be measured with the participant standing relaxed with hands hanging at her sides on the exhale. The tension-controlled measurement tape will be placed directly on the skin, horizontally around the narrowest part of the torso. If unable to locate the narrowest part of the waist, the participant will be measured 2-3 inches above the navel. The hip circumference will be measured with the participant standing relaxed with hands hanging at her sides on the exhale. The tension-controlled measurement tape will be placed directly on the skin or over the underwear, horizontally around the widest part of the hip/buttocks area.

The participant will undergo a whole body DEXA to measure body composition. The DEXA, routinely used to determine bone mineral density, has gained support in research application for assessing fat and lean body mass in whole body and in specific body regions [23, 24, 25]. Data from each scan will be as follows: percent body fat and % lean tissue, fat and lean mass for total body region as well as defined body zones (trunk, leg, and arms) expressed in grams.

5.4 Randomization / Visit 3

Participants, who are eligible based on results of the biopsy from Visit 2, will be called to schedule their third visit for randomization.

This study will use a 2 x 2 randomized design with all 100 subjects being randomized: 25 will receive both lifestyle intervention and metformin, 25 will receive the lifestyle intervention plus metformin placebo, 25 will receive metformin only, and 25 will receive metformin placebo but no lifestyle intervention. The participants randomized to the lifestyle change portion of the study will also have their first intervention session schedule for the same day as well. Treatments will last 4 months.

At Randomization / Visit 3, the participant will be:

- a) randomized to one of the four intervention groups using the Department of Biostatistics Clinical Trial Conduct Website. See section 7.0 for details.
- b) given prescription to fill the study medication at the pharmacy at MD Anderson Cancer Center.
- c) participant will be provided education on recording and monitoring daily intake of study medication into the Pill Diary. See Appendix M for Pill Diary.

- d) review and report side effects of the study medication.

Once the participant is randomized, the research nurse will notify the pharmacist to inform them of the randomization code in order to keep study staff blinded to assignment to metformin vs. placebo.

In-person toxicity assessments will be performed at the end of the first, second, third, and fourth month (plus or minus 10 days). Phone assessments will be done periodically as needed to assess for adverse effects. At the end of the fourth month of the study, the participant will return for the **Post-Treatment Evaluation** to repeat all measurements (all blood tests, anthropometric assessments, second biopsy, and survey packet) taken at the Screening Visits (1& 2). The participant will also be given a Satisfaction Questionnaire, based on their intervention, in advance to complete and return at this visit.

One year after baseline (+/- 1 month), participants will be contacted to complete a 1 Year Follow-Up Evaluation. This evaluation will include anthropometrics assessments, including a DEXA scan, the survey packet, and blood tests collected from the 4th month visit (see Table 5: Study Parameters for the list of laboratory test to be collected for 1 year Follow-up Evaluation). During this visit, the participant will also be compensated with a parking voucher to cover the cost of parking during the visit.

